## **11.2 Protocol Deviations**

Any CSR-reportable protocol deviation will be documented, and its impact on population for any patient will be specified. Numbers and percentages of patients with CSR-reportable protocol deviations will be summarized by deviation type (e.g. major) and category (e.g. noncompliance with study procedures or restrictions). All deviations will be identified prior to database lock and will be summarized and presented in listing(s); listings will include flags for deviation type (major or minor). Major protocol deviations are defined per Guideline for Industry: Structure and Content of Clinical Study from (ICH E3) guidance.

## **11.3 Demographics and Baseline Characteristics**

Demographics and baseline characteristics will be summarized and listed for the Safety Population.

### *11.3.1 Demographics*

Demographic characteristics will include age, age category (2 – 5 years, 6 – 10 years, 11 – 17 years, and  $\geq$  18 years), sex, child-bearing potential, race, and ethnicity. Demographic characteristics will be summarized by cohort and overall. A subject listing of demographics will be provided.

### *11.3.2 Baseline Characteristics*

The following baseline characteristics include baseline weight, height, BMI, BSA, and PD hormones (A4, A4 category [ $<$  ULN;  $\geq$  ULN], ACTH, 17-OHP, and testosterone), and GC regimen. Baseline characteristics will be summarized by cohort and baseline characteristics listing by subject will be provided.

## **11.4 Medical History**

General medical history will be mapped to preferred terms and system organ classes using the Medical Dictionary for Regulatory Activities (MedDRA®) Dictionary (version 24.1). General medical history will be summarized by cohort, system organ class (SOC), and preferred term (PT) for the Safety Population. A subject listing of general medical history will include cohort, start date/end date, verbatim medical history term, SOC, PT, and ongoing status.

# **12 STUDY DRUG AND OTHER MEDICATIONS**

## **12.1 Exposure to Study Drug**

The drug accountability information, including number of tablets dispensed, number of tablets returned, and number of tablets lost or destroyed, nominal tildacerfont dose ([Section 9.4.15.1](#)), and dose adjusted for body weight ([Section 9.4.15.2](#)) will be presented in subject listings.

## **12.2 Prior and Concomitant Medications**

All medication verbatim terms reported on the eCRFs will be mapped according to the World Health Organization (WHO) Drug Dictionary (WHO D Global-B3 Sep2021). The medications will be mapped to Anatomical/Therapeutic/Chemical (ATC) class and preferred names.

All medications will be provided in a subject listing with variables including, but not limited to: Start date/end date/ongoing, medication name, ATC class and preferred name, indication, dose, unit, form, frequency, and route.

## **12.3 Glucocorticoid Regimen**

Concomitant GC therapy will be summarized for each cohort of the study. The source of GC dosing is the A4-based GC Dose Adjustment eCRF.

Descriptive statistics for GC dose (in mg HCe) and BSA-adjusted GC dose will be summarized by cohort and scheduled time point. In addition, the number and percentage of subjects who

decrease their dose of GC regimen will be summarized by cohort. All the above information will be included in a subject listing.

## 13 EFFICACY ANALYSES

The efficacy analyses will exclude data collected under Protocol v3.0.

The efficacy analyses are planned after all subjects have completed the study treatment and the database is frozen. The scheduled visits included in this treatment period can be found in [Table 7](#).

### 13.1 Secondary Efficacy Analysis

The secondary “treatment policy” estimands are evaluated by two secondary efficacy assessments.

#### 13.1.1 Reduction in A4 or Reduction in GC Dosing at Week 12

Population: The analysis population for the secondary efficacy analyses is the PD analysis set.

Variable: The analysis variable is the proportion of subjects in the PD analysis set who are responders (defined in [Table 5](#)). This proportion is calculated for each cohort as the number of subjects at Week 12 (at Week 4 for cohorts 4 through 9) who have a reduction of A4 or reduction in GC reduction, divided by the total number of subjects in the PD analysis who were enrolled in each cohort. This proportion is also calculated to evaluate the overall subjects at Week 12 (at Week 4 for cohorts 4 through 9) by pooling the responders and dividing by the total number of subjects in the PD analysis set.

Subjects with missing A4 or GC dosing information at a given visit are assumed to be non-responders at that visit. Subjects who do not have a reduction from baseline in A4 or a reduction in GC dose are considered non-responders.

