3. STUDY DESIGN

3.1. Overall Design

This is a Phase 2, open-label, dose-ranging study designed to provide safety, efficacy, and PK of tildacerfont, as well as the impact of tildacerfont on adrenal androgens and GC requirements in participants with classic CAH.

Three staggered cohorts (Cohorts 1-3) are planned to investigate QD dosing over 12 weeks of treatment, with an additional optional Cohort 1a, dependent on accumulating safety data. The study is expected to enroll approximately 20 children across the first 3 cohorts (i.e., Cohorts 1, 2, and 3), 10 in the 11-to 17-year age group and 10 in the 2-to 10- year age group. If the optional Cohort 1a is initiated (up to 5 participants), however, Cohorts 1 to 3 may enroll up to 25 children total, 15 in the 11-to 17-year-old age group and 10 in the 2-to 10-year-old age group.

Up to an additional six cohorts (Cohorts 4-9) are planned to investigate BID dosing over 4 weeks of treatment. The study will also enroll up to approximately 15 adults aged ≥ 18 years across Cohorts 4 and 5; and up to approximately 30 children across 4 additional cohorts [up to 15 in the 11- to 17-year age group (Cohorts 6 and 8) and up to 15 in the 2- to 10-year age group (Cohorts 7 and 9)].

If all possible doses are studied, total sample size of this study may be up to approximately 55 children and 15 adults ([Table 1](#)).

Participants enter the study on their current GC regimen (note: dexamethasone is excluded). In Cohorts 1-3, GC dose may be adjusted based on A4 levels at specified weeks and at any visit during the extension. In Cohorts 4-9, there will be no GC adjustment during the 4-week study period, but GC doses can be adjusted for those who participate in the optional extension at Week 4 and any subsequent visit. For further details refer to [Section 5.3.1.2](#).

Cohorts 1 to 3:

Cohorts 1, 1a (if indicated), and 2 will include children ages 11- to 17-years old (up to approximately 5 participants in each cohort), and Cohort 3 (up to approximately 10 participants) will include children ages 2- to 10-years old.

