The study will last approximately 10 weeks including a 2-week Screening Period, a 4-week Treatment Period and a Safety Follow-up visit 30 days after the last dose of study drug). Participants may continue in an extension period upon completion of the 4-week Treatment Period. If participants enroll in the extension after the 4-week Treatment Period, the Safety Follow-up Visit will occur 30 days after the last dose in the extension. Cohorts 4 and 5 will include adults aged ≥ 18 years (up to approximately 5 participants in Cohort 4 and 10 participants in Cohort 5). The 10 participants that may be evaluated in Cohort 5 is to allow for the possibility of more than one dose tested (i.e., 300mg or 400mg BID – per DMC recommendation). Cohorts 6 and 8 will include children ages 11 to 17 years old (up to approximately 5 participants in each cohort) and Cohorts 7 and 9 will include children ages 2 to 10 years old (up to approximately 5 participants in each cohort). Cohorts 8 and 9 may include approximately 5 additional participants each if more than one dose is tested (i.e., 300mg and 400mg equivalent BID). For example, if 5 children are treated with 300mg BID in Cohort 8, the DMC may review safety data from all 5 after 4 weeks of treatment and make a recommendation regarding enrolling another approximately 5 children at 400mg BID ([Table 1](#), [Figure 2](#)).

SPR001-205

Spruce Biosciences, Inc.

CLINICAL STUDY PROTOCOL

Version 5.0

Cohorts 4 and 6 will begin simultaneously with a dose of 200 mg BID in participants aged ≥ 18 years and 200 mg adult equivalent BID in participants aged 11-17 years (200 mg BID has been previously evaluated in adults in study SPR001-202).

The DMC will convene once 4 weeks of safety data is available for 4 sentinels from Cohorts 4 and 6 combined. After reviewing data from these 4 participants (in addition to all other available safety data), the DMC will make a recommendation regarding initiation of Cohorts 5 and 7.

Cohort 5 will enroll adult participants at 300 or 400mg BID (per DMC recommendation) and will provide safety data in adults to support the administration of higher BID doses (i.e., up to 400mg BID) in children and adolescents. Cohort 7 may begin simultaneously with Cohort 5 and will enroll children aged 2-10 years at a dose of 200mg adult equivalent BID.

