8.3. Statistical Analyses

8.3.1. General Considerations

All individual data will be listed as measured. All statistical summaries and analyses will be performed using SAS software (SAS Institute Inc, Cary, North Carolina, USA).

All continuous variables will be presented using an 8-point descriptive summary (n, mean, standard deviation, median, interquartile range [25th percentile, 75th percentile], minimum, and maximum) by dose, as available. Categorical variables will be summarized by frequency and by percentage of participants in corresponding categories.

Any changes to the protocol-specified analyses will be pre-specified in the SAP before database lock.

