## 5 STUDY DESIGN

This is a Phase 2 open-label study with up to 10 cohorts that will evaluate the safety, efficacy, and PK of different tildacerfont dosing regimens potentially up to 200mg once daily (QD), in Cohorts 1-3, for 12 weeks in children with classic CAH, and up to 400mg BID, in Cohorts 4-9, for 4 weeks in children and adults with classic CAH.

Cohorts 1 and 1a (if indicated) in children aged 11-17 years, Cohort 2 in children aged 11-17 years, and Cohort 3 in children aged 2-10 years will study weight-based dose equivalents of up to 200mg QD. Treatment in Cohorts 1-3 will be for 12 weeks. Cohorts 4 and 5 in adults, Cohorts 6 and 8 in children aged 11-17 years, and Cohorts 7 and 9 in children aged 2-10 years will evaluate doses higher than 200mg QD that will be administered BID for 4 weeks.

Cohort 4 (adults) and Cohort 6 (11-17 years) will initiate concurrently at 200mg BID (200 mg BID has been previously evaluated in adults in study SPR001-201). Upon completion of the 4-week dosing on 4 sentinel subjects from Cohorts 4 and 6 combined, the DMC will assess safety data and provide recommendations on continued dosing. If the DMC assesses it to be safe to proceed to a higher dose, Cohort 5 (adults) may be initiated at 300mg or 400mg BID and Cohort 7 (2-10 years) may be initiated at 200mg BID. Following the completion of the 4-week

dosing periods for Cohorts 5 and 7, the DMC will review safety data from 4 sentinel subjects and offer recommendations on whether to proceed to Cohort 8 (11-17 years) and at what dose (300mg or 400mg BID). Following completion of the 4-week dosing period for 4 sentinel subjects in Cohort 8, the DMC will review the safety data and provide a recommendation on whether to proceed with Cohort 9 and at what dose (300mg or 400mg BID) ([Table 1](#)).

**Table 1** Study Cohorts

Cohort	Age	Sample Size	Corresponding Adult Dose	Treatment Duration
1	11-to 17-years	5	50 mg QD	12 Weeks
1a a	11-to 17-years	5	To be determined based on DMC recommendation (50 or 100 mg QD)	
2	11-to 17-years	5	200 mg QD	
3	2-to 10-years	10	50 mg QD, 100 mg QD, OR 200 mg QD	
4	>18-years	5	200 mg BID	4 weeks
5	>18-years	5+5 c	300 and/or 400 mg BID	
6	11- to 17-years	5	200 mg BID	
7	2- to 10-years	5	200 mg BID	
8 b	11- to 17-years	5+5 c	300 and/or 400 mg BID	
9	2- to 10-years	5+5 c	300 and/or 400 mg BID	
		Up to 70 subjects total		

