## 7 SAMPLE SIZE AND POWER

No formal sample size calculation was performed. A sample size of up to approximately 55 children (i.e., 30 children 11- to 17-years of age, and 25 children 2- to 10-years), will provide adequate data to assess the initial safety of tildacerfont in a pediatric population and provide data to support the continued use of the PBPK model to determine pediatric dosing requirements in future studies. Although this is a pediatric study, up to 15 adults are included in this study to allow for all new dosing regimens to be tested in adults prior to children. The safety profile of tildacerfont in adults will primarily be established in other studies.

The study is expected to enroll approximately 20 children across the first 3 cohorts (i.e., Cohorts 1, 2, and 3), 10 in the 11-to 17- year age group and 10 in the 2-to 10- year age group. If the optional Cohort 1a is initiated (up to 5 subjects), however, Cohorts 1 to 3 may enroll up to 25 children total, 15 in the 11-to 17-year-old age group and 10 in the 2-to 10-year-old age group. Up to an additional six cohorts (Cohorts 4-9) are planned to investigate BID dosing over 4 weeks of treatment. The study will also enroll up to approximately 15 adults aged  $\geq 18$  years across Cohorts 4 and 5; and up to approximately 30 children across 4 additional cohorts [up to 15 in the 11- to 17-year age group (Cohorts 6 and 8) and up to 15 in the 2- to 10-year age group (Cohorts 7 and 9)]. If all possible doses are studied, total sample size of this study may be up to approximately 55 children and 15 adults. Up to a total 70 subjects will be enrolled in the study. Please see [Table 1](#) for subject numbers by dosing cohort:

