## **14 SAFETY ANALYSIS**

The Safety Population will be assessed for AEs, SAEs, AEs leading to discontinuation/withdrawal, DLTs, AESIs, physical examination, vital signs, ECGs, and clinical laboratory tests. All analyses of the safety data will be performed by adult equivalent dose levels. Urinalysis, psychiatric evaluations, and concomitant medications will be presented in listings only.

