## **14.2 Clinical Laboratory Evaluation**

Laboratory parameters chemistry, hematology, coagulation, and thyroid panel will be displayed in summary tables by cohort and scheduled time point and will include both observed values and change from baseline values. As applicable, a summary of laboratory parameters will also be displayed in a shift table of baseline values relative to normal ranges (low, normal, high, missing). Subject-level listings for urinalysis and all laboratory parameters (see [Table 12](#)) will be provided. A separate listing will include abnormal clinical laboratory test results. In addition, subjects concurrently meeting the following Hy's law criteria at any assessment date will be identified and listed:

- Alanine aminotransferase (ALT)  $> 3 \times$  ULN
- Aspartate aminotransferase (AST)  $> 3 \times$  ULN
- Total bilirubin (TBL)  $> 2 \times$  ULN

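### If 300 and 400 mg BID are both enrolled in Cohort 5, 8 or 9, the by-cohort responder tables merge the two doses; the SAP also contradicts itself on whether laboratory, vital-sign and ECG tables are by cohort or by dose

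*SAP*

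**What the plan says.** Protocol 3.1 describes the trial in these words: "This is a Phase 2, open-label, dose-ranging study designed to provide safety, efficacy, and PK of tildacerfont". SAP Table 1 (Section 5) assigns Cohorts 5, 8 and 9 "300 and/or 400 mg BID", each with 5+5 subjects. Its footnote explains that the second 5 make room for the other dose if the DMC indicates it. Protocol 3.1 says the same of the paediatric cohorts: "Cohorts 8 and 9 may include approximately 5 additional participants each if more than one dose is tested".

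The efficacy outputs are organised as follows.

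- SAP 13.1.1, composite of A4 or GC reduction: "This proportion is calculated for each cohort", with a pooled overall figure.
- SAP 13.1.1.1: exact intervals for the study and for each cohort, and bar charts with a single bar per cohort.
- SAP 13.1.2, A4 reduction in subjects with elevated baseline A4: per cohort.
- SAP 13.2.3, any reduction, reduction of at least half, and normalisation: overall, per cohort and per subgroup. Section 10.7 defines only two subgroup factors, baseline A4 and sex.
- SAP 13.2.1, continuous PD markers: per cohort, time point and subgroup.

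Two other places point to dose. Protocol 8.3.1 presents continuous variables "by dose, as available", and SAP 9.4.13 computes geometric mean ratios for each cohort and dose level.

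For safety, SAP 14 opens with the rule "All analyses of the safety data will be performed by adult equivalent dose levels". SAP 5.3.1 and protocol 8.3.4 state the same rule, name 300 and 400 mg BID as levels, and include laboratory, vital-sign and ECG tables. Yet SAP 14.2 says laboratory parameters "will be displayed in summary tables by cohort and scheduled time point", and 14.3 and 14.4 are also written by cohort, including the QTcF outlier counts. Only the adverse event tables in 14.1 are specified both ways.

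**The concern.** Cohort stands in for dose only when a cohort has one dose. Cohorts 5, 8 and 9 are built so that they may have two. A programmer following Section 13 would then produce one responder row per cohort, and nothing in that row would show which dose produced the responses. The BID cohorts exist to explore doses above 200 mg QD, so this is the comparison that a reader of a dose-ranging study will look for.

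For safety, the question is which instruction the tables will follow. If they were built from 14.2 to 14.4 alone, 300 and 400 mg subjects in one cohort would share a row for liver tests and QTcF. Protocol 1.3 names both areas as risks: QTcF trends in pre-clinical work and reversible liver enzyme elevations in clinical studies. The SAP does not say whether the general rule or the subsections prevail.

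**Working it through.** **The plan's own total.** SAP Table 1 in cohort order (1, 1a, 2, 3, 4, 5, 6, 7, 8, 9): 5 + 5 + 5 + 10 + 5 + 10 + 5 + 5 + 10 + 10 = 70. By age: adults 5 + 10 = 15; 11 to 17 years 5 + 5 + 5 + 5 + 10 = 30; 2 to 10 years 10 + 5 + 10 = 25. All match SAP Section 7. There is no power calculation to reproduce: "No formal sample size calculation was performed".

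**How many subjects could be in mixed-dose cohorts.** Cohorts 5, 8 and 9: 10 + 10 + 10 = 30. Of all subjects, 30/70 = 43%. The BID cohorts (4 to 9) hold 5 + 10 + 5 + 5 + 10 + 10 = 45, so 30/45 = 67%. These are maxima, reached only if both doses run in all three cohorts. If a cohort uses one dose, nothing in it is merged.

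**What a merged row hides.** The SAP's interval is Clopper-Pearson: lower limit = Beta quantile 0.025 with parameters (x, n − x + 1); upper limit = Beta quantile 0.975 with parameters (x + 1, n − x). The documents give no expected responder rates, so these counts are assumed for illustration only.

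| Row | Responders | Rate | 95% interval |
|---|---|---|---|
| Cohort, doses merged | 5/10 | 50% | 18.7% to 81.3% |
| 300 mg within cohort | 1/5 | 20% | 0.5% to 71.6% |
| 400 mg within cohort | 4/5 | 80% | 28.4% to 99.5% |

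The merged 5/10 would be identical for any of the six splits: 0+5, 1+4, 2+3, 3+2, 4+1 or 5+0. At the extremes, 0/5 has an interval of 0% to 52.2% and 5/5 one of 47.8% to 100%. The row cannot tell these apart.

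**The grouping instructions side by side.**

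| Output | Section that specifies it | Other rule that applies |
|---|---|---|
| Responder proportions, intervals, bars | SAP 13.1.1, 13.1.1.1, 13.1.2, 13.2.3: never dose | None |
| Continuous PD summaries | SAP 13.2.1: cohort | Protocol 8.3.1: dose; SAP 9.4.13: cohort and dose for the geometric mean ratio |
| Adverse events | SAP 14.1: dose and cohort | Agrees with SAP 14 opening |
| Laboratory, vital signs, ECG | SAP 14.2 to 14.4: cohort | SAP 14 opening, SAP 5.3.1, protocol 8.3.4: dose |

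The first row is a gap, because no text anywhere supplies a dose split. The second and fourth rows are contradictions. SAP 15 lists no change from by-dose presentation. SAP 4 lets the SAP prevail over the protocol, so the protocol's rule cannot be relied on to settle the second row.

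One detail on the charts: the bar chart is written for Week 12, while 13.1.1 substitutes Week 4 for Cohorts 4 to 9. The merging applies to the chart only if the BID cohorts are drawn on it.

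**The case against.** The strongest reply has four parts.

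First, a reader might infer that laboratory, vital-sign and ECG data will be summarised by cohort alone, so that a 400 mg signal is diluted. The documents do not support that. Two SAP sections and the protocol require safety summaries by adult-equivalent dose, and nothing says 14.2 to 14.4 override them. Laboratory and ECG data are also listed by subject. This part of the reply stands: it is an inconsistency, not a plan to merge doses.

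Second, a reader might infer that the responder tables breach protocol 8.3.1. They do not. The by-dose phrase there attaches to continuous variables, and the sentence on categorical variables does not mention dose. Protocol 8.3.6 asks for the reduction proportions with baseline-A4 subgroups and is also silent on dose. This stands too. For responders the case rests on the dose-ranging purpose and on the cohort structure.

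Third, the merging is conditional. Cohorts 8 and 9 are adaptive, and the second group of 5 in each of the three cohorts is optional. That is true, but Table 1 provides for this case, so the analysis plan should cover it.

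Fourth, the groups are tiny and the SAP calls the study exploratory. The illustrative intervals for 1/5 and 4/5 overlap widely, and 9.4.13 already gives the A4 geometric mean ratio by dose. This limits the value of splitting but does not remove it. The responder proportions are the secondary efficacy endpoints, and a reader should be able to see them for each dose.

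**Conclusion.** The point holds in two parts.

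1. Should both BID doses be enrolled in Cohort 5, 8 or 9, the responder outputs in SAP 13.1.1, 13.1.1.1, 13.1.2 and 13.2.3 would combine them. Section 13.2.1 is written the same way for continuous PD markers, in tension with protocol 8.3.1 and SAP 9.4.13. At most 30 of 70 subjects are affected.
2. SAP 14.2 to 14.4 conflict with the opening of SAP 14, SAP 5.3.1 and protocol 8.3.4, and the passages must be reconciled.

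The adverse event tables, which carry the primary endpoint, are already specified by dose and are not affected. The size estimate assumes that Table 1 is filled as planned and that both doses are used in all three cohorts; with one dose per cohort the first part has no effect. No claim is made about the actual responder rates. With about 5 subjects per dose within a cohort, no formal dose-response conclusion would follow from the split either.

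**What to change.** 1. In SAP 13.1.1, 13.1.1.1 (text and bar charts), 13.1.2, 13.2.1 and 13.2.3, specify reporting per cohort and adult-equivalent dose level, with Cohorts 5, 8 and 9 split by dose whenever both doses are used. Section 9.4.13 already has this layout. Each sentence needs its own edit, because the grouping is worded differently from one to the next; a global replacement of one phrase would miss the main responder text and the charts.
2. In SAP 14.2 to 14.4, including the QTcF outlier counts, provide the summaries by adult-equivalent dose and also by cohort, as 14.1 does. This follows the rule at the head of Section 14 and keeps the cohort view.

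The cost is SAP wording and additional table columns; trial conduct and data collection do not change. The downside is cells of about 5 subjects with wide intervals. A sentence stating that the by-dose rows are descriptive would guard against over-reading them. The changes should be made before database lock, so that the split is pre-specified.

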2. OBJECTIVES AND ENDPOINTS

COHORTS 1-3 (12-week Treatment)	
Objectives	Endpoints
Primary	
To evaluate the safety of tildacerfont in participants with CAH	AEs and SAEs
Secondary	
To determine the efficacy of tildacerfont on disease control or reduction of GC use in participants with classic CAH during 12 weeks of treatment	Proportion of participants who achieve a reduction in A4 or reduction in GC dosing during treatment period
To determine the efficacy of tildacerfont on disease control in participants with classic CAH after 4 or 12 weeks of treatment	Proportion of participants with elevated baseline A4 who achieve a reduction in A4 at Week 4
	Proportion of participants with elevated baseline A4 who achieve A4 normalization at Week 4 or Week 12
To determine the consistency of preliminary tildacerfont PK in participants with those simulated in a PBPK model	Tildacerfont plasma concentrations will be compared with the current PBPK simulation for consistency
Exploratory	
To explore changes in pharmacodynamic (PD) biomarkers in participants with CAH	Change from baseline in adrenocorticotrophic hormone (ACTH), 17hydroxyprogesterone (17-OHP), A4, testosterone, and 11-ketotestosterone (11KT)
COHORTS 4, 5, 6, 8, 7, and 9 (4-week Treatment)	
Objectives	Endpoints
Primary	
To evaluate the safety of tildacerfont in participants with CAH	Adverse events (AEs) and serious adverse events (SAEs)

Secondary	
To determine the efficacy of tildacerfont on disease control in participants with classic CAH after 4 weeks of treatment	Proportion of participants who achieve reduction in androstenedione (A4) at Week 4
	Proportion of patients who achieve A4 normalization at Week 4.
To determine the consistency of preliminary tildacerfont pharmacokinetics (PK) in participants with those simulated in a physiologically based PK (PBPK) model	Tildacerfont plasma concentrations will be compared with the current PBPK simulation for consistency
Exploratory	
To explore changes in pharmacodynamic (PD) biomarkers in participants with CAH	Change from baseline in adrenocorticotropic hormone (ACTH), 17hydroxyprogesterone (17-OHP), A4, testosterone, and 11-ketotestosterone (11KT)
EXTENSION (Cohorts 1-9)	
Objectives	Endpoints
Primary	
To evaluate the safety of tildacerfont in participants with CAH	AEs and SAEs
Secondary	

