8.3.6. Pharmacodynamic Analyses

The PD Population will be used for all PD analyses.

Change from baseline in PD biomarkers, ACTH, 17-OHP, A4, testosterone, and 11KT will be summarized descriptively using the 8-point summary as well as geometric mean ratios comparing baseline to post baseline, as appropriate. T will be summarized separately for males and females.

Change from baseline in select PD ratios will also be summarized, A4/T (males only) and 11KT/T (males and females, separately). Other ratios may be identified in the statistical analysis plan.

The proportion of participants with a reduction in biomarkers at Weeks 4 (all cohorts) and 12 (Cohorts 1 to 3 only) will be summarized descriptively, including by subgroup, baseline A4 \leq ULN, Baseline A4 $>$ ULN:

- Any reduction
- \geq 50% reduction
- A4 \leq ULN

Change from baseline in GC total daily dose at Week 12 and during the extension period will be summarized descriptively:

- Absolute change (mg)
- Absolute change adjusted for body surface area (mg/m²)
- Percent change (%)
- Proportion of participants with GC reduction
- Proportion of participants with baseline dosing $>$ 3x daily who decrease frequency of administration \leq 3x daily

The proportion of participant with a \geq 1 mg/m² GC reduction or any reduction from baseline in A4 at Week 12 will be summarized descriptively.

Changes in adrenal biomarkers and GC will be summarized in a similar manner for the extension period.

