#### 6.1.2 Secondary

Secondary objectives for Cohorts 1-3 are to characterize the efficacy of tildacerfont in reducing A4 levels after 4 and 12 weeks of treatment and reducing GC dosing after 12 weeks of treatment. The associated secondary endpoints are the proportion of subjects with a reduction from baseline in A4 or a reduction in GC dosing at Week 12; and the proportion of subjects elevated baseline A4 (baseline A4  $>$  ULN) who achieve a reduction in A4 at Week 4 or who achieve normalization of A4 at Week 4 or Week 12.

Secondary objectives for Cohorts 4-9 are to characterize the efficacy of tildacerfont in reducing A4 levels after 4 weeks of treatment. The associated secondary endpoints are the proportion of subjects with a reduction from baseline in A4 or normalization of A4 at Week 4.

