#### 9.4.14 Responder Definitions

The second secondary efficacy and exploratory variables are proportions of responders based on serum PD assessments and GC dosing. Indicator variables for each responder criteria are defined in [Table 5](#).

**Table 5** Responder Definition by Endpoint

Endpoint	Definition	
Composite: Proportion of subjects who achieve reduction in A4 OR reduction in GC dosing (Cohorts 1 through 3) at a postbaseline visit	1	Reduction in A4 OR reduction in GC Dose
	0	(no reduction in A4 AND no reduction in GC Dose) OR missing
Proportion of subjects with elevated baseline A4 who achieve a reduction in A4 at a post-baseline visit	1	Baseline A4 > ULN AND reduction in A4
	0	Baseline A4 ≤ ULN OR no reduction in A4 OR missing
Any reduction at a postbaseline visit	1	Reduction from baseline
	0	No reduction from baseline OR missing
≥ 50% reduction at a postbaseline visit	1	≥ 50% reduction from baseline
	0	< 50% reduction from baseline OR missing
≤ ULN at a post-baseline visit	1	≤ ULN
	0	> ULN OR missing

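### SAP 13.1.1 gives the Cohorts 1-3 A4-or-GC composite to Cohorts 4-9 as well, and pools Week 12 and Week 4 results into one overall rate that matches no stated endpoint

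*SAP*

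**What the plan says.** Protocol Section 2 sets different secondary endpoints for the two parts of the study. Cohorts 1-3 have the composite: "Proportion of participants who achieve a reduction in A4 or reduction in GC dosing during treatment period". Cohorts 4-9 have "Proportion of participants who achieve reduction in androstenedione (A4) at Week 4", with A4 normalization at Week 4 as a separate endpoint and no GC component. Protocol 8.3.6 analyses the composite at Week 12 only ("or any reduction from baseline in A4 at Week 12 will be summarized descriptively"). Protocol 3.1 explains why GC has no place in the second endpoint: "In Cohorts 4-9, there will be no GC adjustment during the 4-week study period".

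The SAP's definitions keep that split. SAP 6.1.2 says of Cohorts 4-9: "The associated secondary endpoints are the proportion of subjects with a reduction from baseline in A4 or normalization of A4 at Week 4". SAP Table 5 (9.4.14) labels the composite responder as A4 reduction or "reduction in GC dosing (Cohorts 1 through 3) at a postbaseline visit".

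SAP 13.1.1 does not keep it. The per-cohort numerator counts those "at Week 12 (at Week 4 for cohorts 4 through 9) who have a reduction of A4 or reduction in GC reduction". A further proportion is "calculated to evaluate the overall subjects at Week 12 (at Week 4 for cohorts 4 through 9) by pooling the responders", with everyone in the PD analysis set as its denominator. SAP 13.1.1.1 reports the results for the study and for each cohort with exact 95% intervals. Table 3 row 5.1 sends the Cohorts 4-9 A4 endpoint to this same section. Section 15, which lists changes from the protocol analyses, does not mention it, and Section 4 makes the SAP prevail where the two documents disagree.

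**The concern.** A programmer following 13.1.1 will produce one study-wide response rate with a confidence interval. It combines a 12-week composite, with GC adjusted by A4 level along the way, and a 4-week result with GC held fixed. It also combines once-daily and twice-daily regimens, and populations selected differently: inclusion criterion 4 asks for A4 between 1.2 and 4 times ULN in Cohorts 4-9 (exceptions with Medical Monitor approval) and sets no A4 limit for Cohorts 1-3.

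The two groups do not have the same routes to a response. In Cohorts 1-3 the algorithm in Protocol 5.3.1.2 calls for a GC reduction when A4 is at or below ULN at Week 4 or 8, so a subject can respond through the GC limb. Cohorts 4-9 have no such route during treatment. The overall figure would be a mixture whose weights are set by how many subjects each part happens to enrol, and it could be quoted as the study's secondary efficacy result.

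**Working it through.** **Sample size behind the pooled rate.** From SAP Table 1, Cohorts 1, 1a, 2 and 3 give 5 + 5 + 5 + 10 = 25, and Cohorts 4 to 9 give 5 + 10 + 5 + 5 + 10 + 10 = 45. The sum is 70, which reproduces the stated maximum. The documents give no expected response rate, power or precision for this endpoint.

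**Weights.** The pooled rate is (n1·p1 + n2·p2)/(n1 + n2), where group 1 is Cohorts 1-3 and group 2 is Cohorts 4-9. The weight on Cohorts 1-3 is:

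- 25/70 = 35.7% at full enrolment
- 20/65 = 30.8% without Cohort 1a
- 20/50 = 40.0% without Cohort 1a and without the optional extra five in Cohorts 5, 8 and 9
- 20/30 = 66.7% if only ten twice-daily subjects enrol, for example Cohorts 4 and 6 alone

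Cohort 1a is optional and the cohorts after 4 and 6 depend on DMC review, so these weights are not fixed in advance.

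**Size of the effect (assumed rates).** Let the A4-reduction probability be a in every cohort, and let an independent GC-reduction probability g apply in Cohorts 1-3 only. Then p1 = 1 - (1 - a)(1 - g) and p2 = a. With a = 50%:

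| g | Cohorts 1-3 | Cohorts 4-9 | Pooled, 25 and 45 | Pooled, 20 and 10 |
|---|---|---|---|---|
| 0% | 50% | 50% | 50.0% | 50.0% |
| 20% | 60% | 50% | 53.6% | 56.7% |
| 40% | 70% | 50% | 57.1% | 63.3% |

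Worked for the last row: (25 × 0.70 + 45 × 0.50)/70 = 40/70 = 57.1%, and (20 × 0.70 + 10 × 0.50)/30 = 19/30 = 63.3%. The effect on A4 is identical in all cohorts, yet the overall rate differs by 6.2 percentage points between two enrolment patterns.

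With g = 40% and a = 40%, the two parts are 64% and 40%, and the pooled rate is 48.6% or 56.0%. With g = 40% and a = 60%, they are 76% and 60%, and it is 65.7% or 70.7%.

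**What happens within Cohorts 4-9.** SAP 9.4.17.4 takes the Day 1 GC dose to be the same as the Week 4 dose. The GC change at Week 4 is therefore zero by construction, and the GC limb adds no responder. What remains is the missing-data rule: 13.1.1 makes a subject a non-responder if A4 or GC information is missing at the visit. A subject with a measured A4 reduction but no GC record at Week 4 counts as a failure here and as a success under the protocol endpoint.

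The GC dose comes from the A4-based GC Dose Adjustment eCRF (SAP 9.4.17.3 and 12.3), and in Cohorts 4-9 the Week 4 adjustment applies only to subjects entering the extension (Protocol Appendix 3, note 10). The documents do not say whether that form is completed for the others, so the number affected cannot be estimated.

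**The case against.** Several points on the other side stand. SAP 13.1.1 defers to Table 5 for its responder definition, and Table 5 labels the composite as Cohorts 1-3; with 6.1.2, this suggests that A4 reduction was intended for Cohorts 4-9 and that 13.1.1 is loosely worded. Every cohort is also reported with its own interval, so a reader can recover either group. SAP Section 7 states that no formal sample size calculation was made, 10.5 calls the study exploratory, and no decision rule depends on the overall row. The pooling sentence could even be read as two overall rates, one per time point, although its single PD-set denominator tells against that.

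Three stronger readings are tempting, and the documents do not support them:

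- A reader might infer that a GC cut ordered at the Week 4 visit could count as a response in Cohorts 4-9. SAP 9.4.17.4 rules this out, and such changes are in any case advised by telephone after the A4 result arrives and apply only to extension entrants.
- A reader might infer that the Cohorts 4-9 rates are generally wrong. They differ from the protocol endpoint only where A4 is present and GC is missing.
- A reader might infer that the SAP has no A4-only analysis at Week 4. SAP 13.2.3 gives any A4 reduction and normalization with exact intervals, overall, by cohort and by subgroup, and 13.1.2 gives A4 reduction at Week 4 by cohort in subjects with elevated baseline A4. Neither has a GC limb or a missing-GC rule. But 13.2.3 is classed as exploratory, and Table 3 row 5.1 points to 13.1.1 instead.

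These points limit the harm. They do not give the pooled rate a meaning.

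**Conclusion.** The point holds, mainly against the pooled rate. As written, 13.1.1 conflicts with Protocol Section 2, SAP 6.1.2 and SAP Table 5, the departure is not declared in Section 15, and the SAP text would prevail. The overall rate and its exact interval correspond to no endpoint in either document.

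Under a common 50% A4-reduction rate and a GC-reduction rate of up to 40% in Cohorts 1-3, the overall figure sits up to 12.9 points below the Cohorts 1-3 rate at full enrolment (70.0 - 57.1) and up to 13.3 points above the Cohorts 4-9 rate with 20 and 10 enrolled (63.3 - 50.0). These sizes rest on assumed rates and on independence of the two limbs. If GC reductions added no responders and A4 response were equal everywhere, there would be no numerical distortion.

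The departure within Cohorts 4-9 is confined to missing GC data and is of unknown size. Because the analysis is descriptive and per-cohort rates are reported, this is a moderate defect that should be corrected, not one that undermines the study.

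**What to change.** Four changes to the SAP:

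1. Limit the composite in 13.1.1 to Cohorts 1-3 at Week 12.
2. Designate A4 reduction alone at Week 4, already produced by cohort under 13.2.3, as the secondary analysis for Cohorts 4-9, alongside A4 normalization at Week 4.
3. Redirect Table 3 row 5.1 to that analysis.
4. Replace the single overall row with one row for Cohorts 1-3 (Week 12 composite) and one for Cohorts 4-9 (Week 4 A4 reduction).

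Each new row still combines dose levels and age groups, and the second includes adults, so the per-cohort rates should remain the main display. The cost is SAP wording and table layout, plus the loss of one study-wide figure. No new data are needed.
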